2. RATIONALE	
3. THEORETICAL FRAMEWORK	
4. RESEARCH QUESTION/AIM(S)	
5. STUDY DESIGN/METHODS	
6. STUDY SETTING	
7. SAMPLE AND RECRUITMENT	
8. ETHICAL AND REGULATORY COMPLIANCE	
9. DISSEMINATION POLICY	
10. REFERENCES	
11. APPENDICES	

SHORT TITLE/ACRONYM

KEY STUDY CONTACTS

Chief Investigator	[contact]		
Study Co-ordinator	[name]		
	[contact]		
Sponsor	Sherwood Forest Hospitals NHS Foundation Trust.		
Joint-sponsor(s)/co-sponsor(s)	None		
Funder(s)	None		
Key Protocol Contributors	[name] [contact]		
Committees			

STUDY SUMMARY

Study Title	Comparative Analysis of Pain Relief between KAPT Block and Paracervical Block for Outpatient Hysteroscopy Procedures at Kings Mill Hospital	
Internal ref. no. (or short title)	The KAPT-Para Block Trial	-
Study Design	48 patients attending outpatient hysteroscopy, divided into two groups. One group will have Paracervical block, the other group will have KAPT block. Questionnaire will be handed over during and after the procedure to assess the pain scores.	
Study Participants	Patients having outpatient hysteroscopy procedures	-
Planned Size of Sample (if applicable)	48 patients divided in to two groups	-
Follow up duration (if applicable)	N/A	_
Planned Study Period	6 MONTHS from 1 st patient recruitment. September 2024.	-
Formal study end date	January 2025 after all data is collected and analysed.	Commented [ST(FHNFT1]: @[name]
Research Question/Aim(s)	Which local anaesthetic provided more pain relief for outpatient hysteroscopy procedures.	

SHORT TITLE/ACRONYM

ROLE OF STUDY SPONSOR AND FUNDER

ROLES AND RESPONSIBILITIES OF STUDY MANAGEMENT COMMITEES/GROUPS & INDIVIDUALS

PROTOCOL CONTRIBUTORS

[figure not shown]
KEY WORDS:

- 1. Outpatient Hysteroscopy Pain Management
- 2. KAPT Block in Gynaecological Procedures
- 3. Paracervical Block Efficacy
- 4. Local Anaesthesia in Hysteroscopy
- 5. Comparative Analgesia in Gynaecology
- 6. Pain Relief Techniques in Outpatient Gynaecological Procedures

STUDY FLOW CHART

Aim: To determine which method, KAPT Block or Paracervical Block, offers superior pain relief at critical stages of the outpatient hysteroscopy procedure: during cervical dilatation, throughout the procedure, and 10 minutes post-procedure. This will involve a detailed analysis of pain scores at these specific time intervals.

SHORT TITLE/ACRONYM

SHORT TITLE/ACRONYM

STUDY PROTOCOL

Comparative Analysis of Pain Relief between KAPT Block and Paracervical Block for Outpatient Hysteroscopy Procedures at Kings Mill Hospital

1 BACKGROUND

KAPT Block:

The King's Mill Anterior-Posterior and Transverse (KAPT) Block, first described in 2015 and presented in 2016, represents a significant advancement in the field of pain management for gynaecological procedures, particularly outpatient hysteroscopy. This type of paracervical block specifically targets the Lee-Frankenhauser (LF) plexus, a part of the Inferior Hypogastric Plexus (IHP), within the Uterosacral Ligament Complex (USLC). The KAPT Block is strategically applied 1.65-3.3cm distal to the cervical insertion of the USLC, a region dense with nerve fibers. Its precise application effectively denervates the cervix and fundus by transecting the LF plexus under the terminal 2.5cm of the USLC.

The efficacy of the KAPT Block was first demonstrated in a prospective observational study presented at the RCOG World Congress in 2016. In this study involving 37 patients, the KAPT Block showed promising results with a mean pain score of 0.704/10 (SD ± 0.24) for Myosure® procedures and 1.2/10 (SD ± 0.44) for Novasure. Importantly, no procedures had to be abandoned due to pain.

A subsequent prospective study with 73 patients (53 undergoing Myosure® and 20 Novasure® procedures) confirmed these findings. The study reported a mean pain score of 0.41/10 for Myosure® and 0.8/10 for Novasure. Notably, a significant proportion of these patients were pre-menopausal and suffered from dysmenorrhea, highlighting the block's effectiveness across various patient profiles.

Paracervical block:

Paracervical block (PCB) is a widely used local anaesthetic technique in outpatient hysteroscopy, but no single method has been established as unequivocally superior. Despite some uncertainty in the literature regarding its superiority, a meta-analysis of 20 trials involving 2851 participants indicated that paracervical injection significantly reduced pain in women undergoing hysteroscopy as outpatients. Intracervical and paracervical injections of local anaesthetic were found to be effective, while transcervical and topical applications did not show significant pain reduction. The meta-analysis supported the conclusion that paracervical local anaesthetic injection is the best method for pain control in outpatient hysteroscopy. However KAPT Block was not included in this meta-analysis

SHORT TITLE/ACRONYM

2 RATIONALE

1. Randomised control trial to evaluate and compare the pain scores of women undergoing outpatient hysteroscopy when administered either the KAPT Block or Paracervical Block, with an emphasis on understanding the relative efficacy of these two anaesthetic techniques.

2. To determine which method, KAPT Block or Paracervical Block, offers superior pain relief at critical stages of the outpatient hysteroscopy procedure: during cervical dilatation, throughout the procedure, and 10 minutes post-procedure. This will involve a detailed analysis of pain scores at these specific time intervals.

3 THEORETICAL FRAMEWORK

The theoretical framework for the study "Comparative Analysis of Pain Relief between KAPT Block and Paracervical Block for Outpatient Hysteroscopy Procedures" is based on two key anaesthesia techniques:

- KAPT Block: A sophisticated block targeting the Lee-Frankenhauser plexus, KAPT Block is effective in denervating the cervix and fundus. Its efficacy, demonstrated through observational studies, shows promising pain relief outcomes in outpatient hysteroscopy.
- 2. **Paracervical Block (PCB)**: A commonly used technique in outpatient hysteroscopy, PCB's effectiveness is supported by a meta-analysis showing significant pain reduction. Although its superiority is debated, it remains a preferred method for pain control in these procedures.

The study aims to compare effectiveness in pain management for outpatient hysteroscopy, thus addressing the gaps in current understanding and practice.

4 Technique

Paracervical Block Technique:

 The primary technique involves injecting Citanest into the cervical stroma at the cervicovaginal junction. This can be done in two ways:

- Four-point injection at 2, 4, 8, and 10 o'clock positions.
- Two-point injection at 4 and 8 o'clock positions only.

KAPT Block Technique:

 Inject 0.2ml of Citanest directly into the cervical stroma at 6 and 12 o'clock to facilitate grasping with a tenaculum.

 Measure 3cm inferolateral from the external os towards 5 and 7 o'clock on both sides using a Pipelle sampler to locate the Lee-Frankenhauser plexus in the Uterosacral Ligament Complex (USLC).

NHS

Health Research Authority

SHORT TITLE/ACRONYM

 Perform an inject-withdrawal technique, injecting a total of 4ml at the measured sites on each side, distributed as follows:

 - 2ml directly (Anterior to Posterior) at 5 o'clock and 7 o'clock. Sideways elevation of the lower lip of the cervix with a tenaculum can facilitate this step.

 - 2ml from the medial to the lateral aspect at 5 o'clock and 7 o'clock, angling the syringe slightly for ease.

- The depth of injection should be 25mm, approximately $\frac{3}{4}$ of the length of the dental syringe needle.

4. The objective is to infiltrate the LF plexus in both the supero-inferior and lateral planes.

5. Allow a pause of at least 3 minutes before commencing the procedure.

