8.2.2 Sampling technique

Participants will be selected randomly from women attending outpatient hysteroscopy at Kings Mill Hospital. This random sampling approach ensures that the sample is representative of the population receiving these procedures. This strategy aligns with the study's methodological framework, allowing for a fair comparison between the two anaesthetic techniques without bias, and it is reflective of the theoretical framework focusing on pain management in outpatient gynaecological procedures.

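### The paracervical comparator has no fixed variant, volume or wait and is not declared as usual practice, whereas KAPT has a set volume and a minimum wait

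*Protocol*

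**What the plan says.** The protocol's section 4 (Technique) describes both blocks.

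- **Paracervical block.** Citanest goes into the cervical stroma at the cervicovaginal junction, and "This can be done in two ways": "Four-point injection at 2, 4, 8, and 10" o'clock, or "Two-point injection at 4 and 8" o'clock only. No volume, depth or wait follows, and nothing says who chooses the variant or on what basis.
- **KAPT block.** A small infiltration is made at the tenaculum sites. The main injection is at a point measured 3 cm from the external os, 25 mm deep, "injecting a total of 4ml at the measured sites on each side". The last step of the KAPT list reads "Allow a pause of at least 3 minutes before commencing the procedure".

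The purpose is stated in section 2 (Rationale): a randomised trial of pain scores, "with an emphasis on understanding the relative efficacy of these two anaesthetic techniques". Sections 5.1 and 5.2 repeat it, asking which method gives better relief and promising an evaluation of each block technique. Section 1 (Background) says of paracervical block that "no single method has been established as unequivocally superior". Section 9.7 (Indemnity) treats the questionnaire as the only addition to planned care.

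**The concern.** What is injected, where, in what amount and how long before the procedure defines the intervention. Those items belong in the protocol, and a statistical analysis plan would not normally set them. Here they are set for one arm and left open for the other.

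Followed as written, the arms may differ in total dose, number of injection points and time allowed for onset, as well as in where the block is placed. Only KAPT patients are guaranteed a wait. Because no selection rule exists, the operator can also pick the paracervical variant after learning the allocation. At stake is the meaning of the result: whether a difference in pain scores speaks to the relative merit of the two techniques, which is the stated aim, or partly to dose and waiting time.

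**Working it through.** No figure in the plan tests this point. The sample size of 48 neither supports nor refutes it, so the check sets the two descriptions in section 4 side by side.

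| Element | KAPT | Paracervical |
|---|---|---|
| Injection pattern | 5 and 7 o'clock, two directions each | four-point or two-point, no rule |
| Main volume | 4 ml per side | not stated |
| Added infiltration | 0.2 ml at 6 and 12 o'clock | none stated |
| Depth | 25 mm | not stated |
| Wait before procedure | at least 3 minutes | not stated |

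**1. KAPT volume.** Each side receives 2 ml in the anterior-posterior direction and 2 ml from medial to lateral: 2 + 2 = 4 ml per side, which agrees with the plan's own figure. Over two sides this is 2 × 4 = 8 ml. The tenaculum-site infiltration adds 0.2 ml if that is the total, or 2 × 0.2 = 0.4 ml if it is given at each site. The overall volume is therefore 8.2 to 8.4 ml.

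**2. Paracervical volume.** It cannot be computed. To match 8 ml, the four-point variant would need 8 / 4 = 2 ml per point and the two-point variant 8 / 2 = 4 ml per point. The protocol requires neither, so equality of dose is possible but not assured.

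**3. Wait.** The pause is the fifth step of the KAPT list and has no counterpart in the paracervical list. For KAPT it is a floor, not a fixed interval. For the comparator any interval, including none, complies with the text.

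**4. Is the gap filled elsewhere?** The design, sampling, recruitment and protocol-compliance sections and the schedule of procedures give no paracervical variant, volume or wait.

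**5. What the contrast estimates.** Let p be the share of comparator patients given the four-point block. If both variants are used, the expected difference is p × (KAPT minus four-point) + (1 − p) × (KAPT minus two-point). The text allows any p from 0 to 1. This is a valid randomised contrast between packages, but the content of one package is unknown in advance, and the protocol does not ask for the variant given to be recorded.

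**6. Comparison with the aim.** Sections 2, 5.1 and 5.2 ask about the relative efficacy of two techniques. Steps 1 to 3 show that dose and onset time may vary together with technique.

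**The case against.** The strongest reply is that the comparator is meant to be paracervical block as commonly given. Section 1 says that no method is clearly best, section 3 speaks of comparing effectiveness and of gaps in practice, and section 9.7 says that standard care is little altered. A flexible comparator is legitimate in such a trial, and volume, depth and pause are part of KAPT as this protocol defines it. Much of this stands: it is why declaring usual practice is an acceptable remedy. But the protocol never makes the declaration, and sections 2 and 5.2 use the language of efficacy. Even a usual-practice arm needs a record of what was given.

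Staff may in fact wait 3 minutes in both arms. If so, writing it down costs nothing, but at present it is not required.

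A reader might infer more than the documents support:

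- *That no difference could be attributed to technique, or that the trial is biased.* Randomisation protects the comparison of packages, and no bias of known direction or size can be shown.
- *That the fairness claim in section 8.2.2 is contradicted.* That sentence concerns the selection of participants, not standardisation of the blocks.
- *That the two-point variant gives half the dose.* This holds only if volume per point is constant; an operator could equally hold the total constant.
- *That pain at cervical dilatation is the most affected.* The protocol gives no onset time for either block.

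**Conclusion.** The point holds as a specification gap that should be fixed before recruitment. KAPT is set at 8 ml over both sides with a wait of at least 3 minutes. The comparator may be either of two variants with no stated volume or wait, and is not declared as usual practice. The trial can validly compare KAPT as specified with paracervical block as delivered. It can give only a limited answer on relative technique efficacy, because unequal dose or onset time could contribute to any difference.

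The only figures on which this rests are the 8 ml and the 3-minute floor, both from section 4. No effect on pain scores is claimed. Whether to fix one variant or to declare usual practice is partly a design choice for the clinical leads; leaving the matter undeclared, with only one arm required to wait, is the defect.

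**What to change.** In section 4:

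1. Apply the same minimum wait in both arms: at least 3 minutes from the last injection to the start of the procedure.
2. Record for every patient the sites injected, the total Citanest volume and the time from block to dilatation.
3. Before recruitment, choose one of two routes. Either name one paracervical variant and its total volume for all comparator patients, or state that the comparator is usual practice and word the conclusion as KAPT as specified against paracervical block as delivered.

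**Cost.** A short change of protocol wording and three fields on the case form. The wait adds up to about 3 minutes per comparator patient, on the assumption that current practice waits between 0 and 3 minutes; it adds nothing where 3 minutes is already observed. Fixing one variant reduces operator freedom and narrows the result to that variant. Declaring usual practice avoids this, but leaves the result less specific about technique.

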5 RESEARCH QUESTION/AIM(S)

How do the pain relief outcomes of the King's Mill Anterior-Posterior and Transverse (KAPT) Block compare to the Paracervical Block in women undergoing outpatient hysteroscopy procedures **5.1 Objectives**

- To conduct a randomised control trial evaluating and comparing the pain scores of women undergoing outpatient hysteroscopy when administered either the KAPT Block or the Paracervical Block.
- 2. To determine which method, KAPT Block or Paracervical Block, offers superior pain relief at critical stages of the outpatient hysteroscopy procedure: during cervical dilatation, throughout the procedure, and 10 minutes post-procedure, through detailed analysis of pain scores at these specific intervals.

The out patients hysteroscopy procedures will include:

Myosure removal of polyps

Myosure removal of fibroids

Thermablate endometrial ablation

5.2 Outcome

- 1. **Pain Score Comparison**: Determination of differences in pain scores between the KAPT Block and Paracervical Block at three key stages: during cervical dilatation, throughout the hysteroscopy procedure, and 10 minutes post-procedure.
- 2. **Patient Comfort Analysis:** Assessment of patient comfort levels and procedural tolerability with each anaesthetic technique, contributing to patient-centred care in outpatient settings.
- 3. **Clinical Efficacy Evaluation**: Evaluation of the clinical efficacy of each block technique, aiding in evidence-based decision-making for pain management in outpatient hysteroscopy.

6 STUDY DESIGN and METHODS of DATA COLLECTION AND DATA ANALYIS

This study will be a randomized control trial, comparing the efficacy of KAPT Block and Paracervical Block in outpatient hysteroscopy. This approach will provide robust, comparative data on the effectiveness of these anaesthetic techniques.

Data Collection Methods:

Patient Questionnaires with Visual Pain Score: Patients will complete questionnaires with a
visual analogue scale (VAS) to self-report their pain levels at various stages of the procedure
(during cervical dilatation, the procedure itself, and 10 minutes post-procedure). This method
allows for direct, objective assessment of pain from the patient's perspective.

Data Analysis Methods:

Quantitative Analysis: The collected pain scores will be statistically analysed to determine the
effectiveness of each anaesthetic technique. This analysis will involve comparing mean pain
scores and assessing variations in pain experiences among patients.

Data Management:

- Data will be de-identified to maintain patient confidentiality.
- Electronic data will be securely stored and encrypted. Only authorized personnel will have access.
- Hard copies, if any, will be kept in a secure location.
- After the study, data will be archived as per institutional and legal guidelines.

Software: Statistical software will be used for quantitative data analysis.

7 - Patient Public Involvement (PPI)PPI groups have been involved with the study proposal process. A number of patients were asked specific questions regarding the study design and purpose. All information has been stored for future reference and publication.

A total of 10 patients were approached to complete a short questionnaire. The answers to the questionnaire concluded that 100 percent of patients agreed that the study would be beneficial and is an important subject. The vast majority of patients stated they would participate in the study and the information provided is clear and concise.

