8.2 Sampling

8.2.1 Size of sample

The sample size is based on previous studies indicating a significant difference in pain scores between different anaesthetic techniques. Prior research by Noor et al. (2021) showed a noticeable variation in pain scores with a relatively small sample. Our study aims for a sample size of 48 patients, considering a 10% increase to account for potential dropout. This size is determined to achieve adequate power (80%) and a significant level (α error = 0.05), ensuring the study is sufficiently powered to detect meaningful differences in pain scores between the KAPT Block and Paracervical Block.

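### Superiority is to be judged at three co-equal pain stages with no primary stage and no winning rule, so the single alpha of 0.05 and 80% power do not describe that conclusion

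*Protocol*

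**What the plan says.** Objective 2 (Protocol section 5.1) is to find out which block "offers superior pain relief at critical stages of the outpatient hysteroscopy procedure: during cervical dilatation, throughout the procedure, and 10 minutes post-procedure". The same aim appears in the study flow chart and in section 2. Outcome 1 in section 5.2 carries it over as "differences in pain scores between the KAPT Block and Paracervical Block at three key stages". The three stages are always listed side by side. None is called primary, none is ranked above another, and nothing says whether a block must win at one, two or all three, or what follows if the stages favour different blocks.

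The analysis text in section 6 says that mean pain scores will be compared. It names no stage and no joint test.

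Section 8.2.1 sets 80% power and "a significant level (α error = 0.05", once each, "ensuring the study is sufficiently powered to detect meaningful differences in pain scores between the KAPT Block and Paracervical Block". It does not say at which stage. The planned size is "48 patients divided in to two groups" (Study Summary), "considering a 10% increase to account for potential dropout".

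**The concern.** The trial exists to name the better block. A significance level and a power have meaning only for a defined test or decision rule. Here the conclusion can draw on three comparisons, while the design figures are given as if there were one.

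Two things are at stake. If a difference at any single stage is enough to call a block superior, the false-positive rate of that conclusion exceeds 5%. If a difference at every stage is needed, the trial is less likely to reach a conclusion than 80% suggests. The protocol does not say which applies. It also does not say which stage answers the question if, for example, one block does better at dilatation and the other at 10 minutes.

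**Working it through.** **Inputs from the Protocol.** Three stages (5.1, 5.2). Alpha 0.05 and power 80% (8.2.1). Total 48 in two groups (Study Summary). Allowance for dropout 10% (8.2.1).

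**Assumptions, because the Protocol is silent.** Two-sided tests, equal arms, approximately normal test statistics, and the same correlation ρ between every pair of stages, taken from 0 to 0.9.

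**The plan's own figure.** The 48 cannot be rebuilt, because 8.2.1 gives neither a difference nor a standard deviation. Only the dropout step can be checked: 43 / 0.9 = 47.8 and 43 × 1.1 = 47.3, both rounding up to 48. That is consistent with about 43 evaluable patients but does not show which test the size was meant for.

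**Reading A: any one stage is enough.** With independent stages, the chance of at least one false positive is 1 − (1 − 0.05)³ = 1 − 0.8574 = 0.143. For any correlation it cannot exceed 3 × 0.05 = 0.15. With correlation ρ, it is 1 − P(|Z₁|, |Z₂| and |Z₃| all below 1.96) for three equally correlated standard normals:

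| ρ | False claim for either block |
|---|---|
| 0 | 14.3% |
| 0.3 | 13.6% |
| 0.5 | 12.5% |
| 0.7 | 10.9% |
| 0.8 | 9.8% |
| 0.9 | 8.4% |

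Simulated t-tests with 22 and 24 patients per arm agree: about 14.4% at ρ = 0, 12.6% to 12.9% at 0.5, and 8.4% to 8.5% at 0.9. These rates cover a false claim for either block, which fits an aim that asks which of the two is better. A false claim for one given block is about half as likely: 7.3% at ρ = 0 and 4.2% at 0.9, against a nominal 2.5%.

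**Reading B: two of three stages are needed.** With independent stages, 3 × 0.05² × 0.95 + 0.05³ = 0.0071 + 0.0001 = 0.7%. At ρ = 0.9 the rate is 4.4%.

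**Reading C: all three stages are needed.** With independent stages, 0.05³ = 0.01%. At ρ = 0.9 the rate is about 2.3%. Power moves the other way. If each stage alone had 80% power, the chance of winning all three with independent stages would be 0.8³ = 0.512, or 51%. Positive correlation raises this, but it reaches 80% only when ρ = 1.

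**Set against 8.2.1.** Reading A does not keep the stated 5% if each stage is tested at 0.05. Reading C keeps it but loses the stated 80%. Reading B keeps 5% over this range, but its power is again not that of a single test. Section 8.2.1 describes one test at one stage, and no such stage is named.

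**The case against.** The strongest reply is that the Protocol never says that each stage will be tested at 0.05, nor that one win suffices. The 0.05 appears only in the sample-size text and could be read as an overall level, and the objective joins the stages with "and". If two or three stages must win, the error stays below 5%. This stands. A reader might infer that the error of the headline claim is simply two to three times the stated 5%. The documents do not support that, because the figure depends on a decision rule they do not contain.

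Correlation also matters. No value is given. The Study Summary has the questionnaire given during and after the procedure, while section 9.4 has it completed afterwards. Ratings recalled together could be highly correlated, so the range must run up to about 0.9, where Reading A gives 8.4%.

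A reader might also infer a specific loss of power. Taking 22 evaluable per arm, the effect detectable with 80% power is (1.960 + 0.842) × √(2/22) = 0.845 SD, and a Bonferroni level of 0.05/3 = 0.0167 would leave about 66% power. But that effect is back-solved, not stated, and nobody has planned a Bonferroni correction. It is an illustration, not a property of this plan.

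A third inference is that the winning stage can be freely chosen afterwards. All three stages are prespecified, so selective emphasis would be visible to a reader of the protocol. It would, however, break no stated rule.

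Finally, a multiplicity procedure may properly sit in a statistical analysis plan. That is fair for the procedure. It does not cover the choice of the outcome that answers the research question and carries the sample size. The Protocol takes up that choice itself and leaves it at three.

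**Conclusion.** The point holds in conditional form. The Protocol sets three co-equal stages for a superiority conclusion, with no primary stage and no rule for combining them, and states one alpha and one power that attach to none of them.

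The size depends on the rule. If each stage is tested at two-sided 0.05 and any win counts, a false claim for either block has a probability of about 8% to 14%, for assumed correlations from 0.9 to 0. If all three must win, the error is at most about 2.3% over that range, but power is below the single-test 80% unless the stages are perfectly correlated. Neither alternative matches 8.2.1. The absence of a rule is certain; the error rates are conditional on the assumptions given.

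This should be settled before any data are seen, since a primary stage chosen afterwards would carry little weight.

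**What to change.** In section 5.2, the sponsor names one stage as the primary outcome, tested at two-sided 0.05. Pain during the procedure is one example. The documents do not rank the stages, so the choice is the sponsor's.

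The other two stages are tested in a prespecified fixed order, each at 0.05 only if the preceding test is significant. Otherwise they are reported as estimates with 95% confidence intervals only. This keeps the overall false-positive rate at 5% without splitting alpha.

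Section 5.2 should also state that the superiority conclusion rests on the primary stage, and section 8.2.1 that alpha and power refer to that stage.

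The cost is protocol wording. The small downside is that later stages cannot support a formal claim if the first test fails. Naming the stage does not by itself justify 48 patients: that needs a difference and a standard deviation for the chosen stage, which 8.2.1 does not give. This is a separate matter, and it could change the number.

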8.1 Inclusion criteria

- Women attending outpatient hysteroscopy procedures at Kings Mill Hospital.
- Age 18 years and above.
- Willing to participate and able to provide informed consent.

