8.1.2 Exclusion criteria

- Women with known contraindications to local anaesthetics.

- Women with a history of allergic reactions to the anaesthetics used.

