9.4 Patient & Public Involvement

The Patient will complete the Questionnaire following outpatient hysteroscopy which will be the basis of the research to assess the visual pain score.

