12.2 Appendix 2 – Schedule of Procedures (Example)

Procedures	Visit
	Screening
Informed consent	х
Demographics	x
Medical history	х
Treatment	х
Questionnaire	х
Interview	х

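### No pain score is taken before the block although women with pre-existing pelvic pain are eligible, so chance imbalance in arrival pain cannot be seen or adjusted for on the VAS

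*Protocol*

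**What the plan says.** **Timing of the scores.** Section 6 (Data Collection Methods) collects VAS pain "during cervical dilatation, the procedure itself, and 10 minutes post-procedure". The Study Summary says "Questionnaire will be handed over during and after the procedure to assess the pain scores", while section 9.4 says "The Patient will complete the Questionnaire following outpatient hysteroscopy". These two statements differ on timing, but neither puts a score before the block. Appendix 2 ticks a questionnaire in one column headed as screening. The same column also holds treatment, and the table is marked as an example, so it does not establish a pre-block score either.

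**Eligibility.** Section 8.1 takes "Women attending outpatient hysteroscopy procedures at Kings Mill Hospital", aged 18 or over and consenting. Section 8.1.2 has two exclusions: "Women with known contraindications to local anaesthetics" and "Women with a history of allergic reactions to the anaesthetics used". Neither concerns pain on the day.

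**Analysis and allocation.** Section 6 compares mean pain scores and names no covariate. Section 8.3 randomises women to one of the two blocks. It ends with an unfinished note about stratification that names no factor.

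**Background.** Of the second KAPT series, section 1 says "a significant proportion of these patients were pre-menopausal and suffered from dysmenorrhea". Its mean scores were 0.41/10 (Myosure) and 0.8/10 (Novasure).

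**The concern.** The stated question is about pain relief. Each recorded score mixes pain from the procedure, as modified by the block, with any pain the woman brought with her. Without a score on arrival the two cannot be separated. This matters most 10 minutes after the procedure, when the procedural stimulus has ended. The earlier KAPT means quoted in section 1 run from 0.41 to 1.2 out of 10, so if scores are again that low, one or two points of arrival pain would be as large as the means being compared.

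The gap belongs to the protocol rather than to an analysis plan. An analysis plan can choose among covariates that were collected, but it cannot create one. Once the block is in, the measurement is lost.

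At stake are precision and the ability to show that two small arms started from a similar level of pain. The validity of the comparison is not at stake.

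**Working it through.** **1. Women per arm.** Section 8.2.1 gives 48 in total, including 10% for dropout, with 80% power and alpha 0.05. It states no difference and no SD, so 48 cannot be rebuilt forwards. Working back, 43/0.90 = 47.8 and 43 × 1.10 = 47.3 both round up to 48, whereas 44 inflates to 49. So 48 corresponds to about 43 evaluable women. I use 22 per arm for evaluable women and 24 per arm for all women randomised, assuming equal allocation because no ratio is stated.

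**2. Detectable difference.** With 22 per arm and two-sided 0.05 (sidedness is not stated), the normal approximation gives d = (1.960 + 0.842) × sqrt(2/22) = 0.845 SD. This is the reference at which the unadjusted comparison has 80% power.

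**3. Chance gap in arrival pain.** In baseline SD units, SE = sqrt(2/n).
- n = 24: sqrt(2/24) = 0.289
- n = 22: sqrt(2/22) = 0.302, with a 95% range of ±1.96 × 0.302 = ±0.59

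At 22 per arm the chance of a gap above 0.3 SD is 32%, and above 0.5 SD it is 10%. At 24 per arm these are 30% and 8%.

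**4. What reaches the outcome.** A baseline gap shifts the outcome difference by r times its size, where r is the within-arm correlation between arrival pain and the later score. For a gap of one SE:
- r = 0.3: 0.3 × 0.289 = 0.087 to 0.3 × 0.302 = 0.091 SD
- r = 0.5: 0.5 × 0.289 = 0.145 to 0.5 × 0.302 = 0.151 SD

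**5. Gain from adjustment.** Residual variance is multiplied by 1 − r². Power is Φ(2.802/sqrt(1 − r²) − 1.960) at d = 0.845 and 22 per arm. The equivalent gain in sample size is 1/(1 − r²) − 1.

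| assumed r | variance cut | power | equivalent extra patients |
|---|---|---|---|
| 0 | 0% | 80% | 0% |
| 0.3 | 9% | 83.6% | 10% |
| 0.5 | 25% | 89.9% | 33% |

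These figures ignore the one degree of freedom spent on the covariate. The protocol gives no value for r, and r may differ between the three time points.

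**6. Is the unadjusted comparison biased?** In 20,000 simulated trials with no true difference, 22 per arm and arrival pain ignored, the mean estimated difference was within 0.003 SD of zero. Type I error was 5.0% to 5.2% for r = 0.3, 0.5 and 0.7.

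**The case against.** The strongest reply is that nothing here is an error. The protocol asks how much pain women report at each stage, and comparing post-block scores between randomised arms answers that validly. Chance imbalance is already part of the ordinary standard error. This stands, and step 6 confirms it.

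A reader might infer that a woman's existing pain is counted as failure of her block. The document does not support this. It defines no block failure, no responder threshold and no change from baseline. Arrival pain raises scores in both arms, and randomisation balances it on average.

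A reader might also infer that arrival pain cannot be adjusted for at all. That goes too far. Appendix 2 lists "Medical history" and demographics, which could support a coarse yes/no adjustment, and the stratification step is still open. Neither would measure how much pain a woman has on the day, so the statement holds only for adjustment on the VAS.

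The evidence that women arrive in pain is weak. Dysmenorrhoea is a history of menstrual pain and not pain on the day. The series in which it was common still had means below 1 out of 10, which suggests little carry-over. No part of the protocol says how many women arrive in pain. If most score zero, a baseline VAS explains little. This limits the likely benefit without removing the case for a measurement that is cheap and cannot be taken later.

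Finally, the choice of covariate is commonly left to the analysis plan, so the lack of a named covariate in section 6 is not itself a fault. Whether the score is collected is settled in the protocol.

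**Conclusion.** The point holds as a cheap improvement in precision. Women with pre-existing pelvic pain may enter, no pain score precedes the block, and a chance difference in arrival pain can therefore be neither described nor corrected on the VAS. A typical chance gap would move the comparison by about 0.09 to 0.15 SD, and adjustment would raise power from 80% to about 84% to 90%. Both ranges assume r of 0.3 to 0.5, equal allocation, 22 to 24 women per arm (22 for the power figures) and a two-sided test. If r is near zero, or most women arrive without pain, the gain is close to nothing. The randomised comparison is unbiased either way.

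**What to change.** Leave eligibility unchanged. In section 6 (Data Collection Methods), add one VAS line completed after consent and before allocation is revealed and the block is given, so that knowing the allocation cannot colour the answer. Bring the Study Summary, section 9.4 and Appendix 2 into line with that timing. In section 6 (Data Analysis Methods), state that pain scores will be compared between arms adjusted for the pre-block VAS. Details can go in the analysis plan.

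The cost is about a minute per woman, one more line on a form already used at the same visit, one sentence of analysis text and one degree of freedom. A yes/no item on analgesics taken that day is optional, since no benefit has been shown for it.
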